14.1.1 Primary Objective: Derivation and analysis of the primary endpoint

No Evidence of Disease activity (NEDA), also referred to as freedom from disease activity, is a new goal that is emerging in MS treatment. NEDA is a composite measure of disease activity, including relapses, cognition and disability progression, and MRI activity.

NEDA-3 during the Extension Study Period is defined as absence of the following three events during the Period:

- Qualifying Relapses
- 6-months Confirmed Disability Progression (6MCDP, see definition below)
- MRI Activity (i.e., presence of T1 Gd+ lesions and/or active T2 lesions)

NEDA-3 will be analyzed with the Kaplan-Meier (KM) time-to-event method to reduce the impact of unknown/missing information.

The start date will be the end date of M24 Visit + 1.

The event date will be defined as the minimum of

- the onset date of the first qualifying relapses during the Extension Study Period
- the start date of the first 6MCDP during the Extension Study Period (see definition below)
- the scan date of the first MRI during the Extension Study Period where at least one T1 Gd+ lesion or at least one active T2 lesion (see Section 9.8 for definition) is identified.

Imputation of partial onset dates of relapses is described in Section 9.7. Since full dates of MRI scan and EDSS assessment are mandatory, partial dates of 6MCDP, or MRI Activity are not expected.

If the participant did not experience any of the three events described above during the Extension Study Period, the minimum of the scan date of the last available MRI, the assessment date of the last available EDSS, and the Extension Study completion/discontinuation date will be used as the censoring date.

The time to disease activity (in months) will be calculated as [event date or censoring date as applicable – start date + 1]/30.4375. The number of participants at risk, failed, and survival rate (i.e., the proportion of participants with NEDA-3) along with the 95% CI will be estimated as per the KM method and reported at 6-months intervals. The KM survival curve will be plotted as well.

A descriptive summary of number and proportion of participants with event (overall and by type of event, i.e., qualifying relapse, 6MCDP, or MRI activity as the earliest event) and censored will be also presented.

6MCDP

The 6MCDP during Extension Study Period is defined as sustained increase in EDSS score that started during the Period. A Sustained Increase in EDSS score is defined by an increase of:

- at least 1.5 points if the Baseline EDSS score was 0, or
- at least 1 point if Baseline EDSS score was between 0.5 and 4.5 inclusively, or
- at least 0.5 point if the Baseline EDSS score was at least 5,

that occurs over a 6-months' time-period.

The increase will be defined as sustained when it occurs on two post-Baseline Visits during the Extension Study Period that are at least 166 days apart (to be consistent with the parent study minimum visit gap) and no observations at any other visits (including unscheduled visits) in between are less than the defined increase. The assessment date of the earlier of the two EDSS assessments with the defined increase will be defined as the start date of 6MCDP.

For descriptive summaries the following rules will be defined:

Qualifying Relapse

- Yes: any qualifying relapse reported during the Extension Study Period,
- No: Extension study period completed, and no qualifying relapse reported during the Extension Study Period,
- Unknown: otherwise.

6MCDP

• Yes: sustained increase in EDSS score that started during the Extension Study Period,

- No: at least 2 post-Baseline EDSS assessments that are 166 (or more) apart and no sustained EDSS progression that started during the Extension Study Period,
- Unknown: Otherwise.

MRI activity

- Yes: any T1-Gd+ or active T2 observed during the Extension Study Period,
- No: at least one post-Baseline MRI and no T1-Gd+ or active T2 observed during the Extension Study Period,
- Unknown: otherwise.

Analysis (Analysis Set)	Derivation	Statistical Analysis Methods	Missing data handling		
	Primary endpoint: Proportion of participants with NEDA-3 during Year 3 Visit and Year 4 Visit Period after the initial dose of cladribine tablets				
Primary (FAS)	Time to event: [event date or censoring date as applicable – start date + 1]/30.4375	KM time-to-event: The number of participants at risk, failed, and survival rate (i.e., the proportion of participants with NEDA-3) along with the 95% CI will be estimated as per the KM method and reported at 6-months intervals. The KM survival curve will be plotted as well.	Imputation for partial dates is described in Section 9.7. Participants experienced no event will be censored as defined above (minimum of the scan date of the last available MRI scan, the assessment date of the last available EDSS, and the study completion/discontinuation date).		

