9.4 Conversion Factors

The following conversion factors will be used to convert days into months or years for all observations except Visit related dates:

- 1 month = 30.4375 days,
- 1 year = 365.25 days.

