9.5 Time Window

- Day 1 is the day of start of study medication at MAGNIFY MS Baseline Visit, the day before is Day -1 (no Day 0 is defined).
- Study day is defined relative to Day 1.

The visit schedule in the Extension Study is defined as follows:

- 1 month = 30 days,
- 1 year = 360 days,

relative to the M24 Visit in the parent study.

- MAGNIFY Extension Baseline Visit: The visit is planned to coincide with or be as near to M24 as possible to minimize the transition gap period, it may also be the same visit as M24.
- Visit 1: 1 year ((360 days) after M24 Visit (\pm 30 days)
- Visit 2: 2 years (720 days) after M24 Visit (± 30 days)

Visit 1 and Visit 2 will also be referred to as the M36 Visit and the M48 Visit, respectively, in the following sections of this IAP as well as in the Tables, Listings, and Figures (TLF) outputs, for consistent presentation of analyses and results over time. Footnotes will be added in the TLF outputs to clarify that these Visits are to be understood as nominal Visits.

In each analysis, should an assessment be delayed, participants' assessment data will be treated as though it occurred at the nominal time point specified (i.e., data collected out of visit windows will not be excluded or adjusted in any analysis) and inferences will be conducted accordingly. Thus, further time windows will not be specified. The MRI assessment will be the only exception to this rule. Handling of out-of-window MRI assessments is discussed in Section 9.8.

All observations from unscheduled visits will be included only in the analyses of visit independent summaries (e.g., counts of AEs, concomitant medications and procedures, relapse reporting and EDSS) unless for the last assessment available. In this case the missing Early Withdrawal (EW) visit will be imputed by the unscheduled visit.

The assessments of the EW visit will be mapped to the nearest planned post-baseline visit with a missing assessment before or after the EW visit of the individual assessment for all statistical analyses and descriptive summaries. As not all assessments of the EW are performed at each visit, the different assessments of the EW can be assigned to different visits. If the duration (in days) between the EW visits and two missing planned visits are equal, then the assessment will be assigned to the later visit.

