9.6 Study Period

Study Periods

The following study periods are defined:

Treatment Period (i.e., Parent Study Period): see MAGNIFY MS IAP version 3.0 for definition.

Course 1 Treatment Period: see MAGNIFY MS IAP version 3.0 for definition.

Course 2 Treatment Period: see MAGNIFY MS IAP version 3.0 for definition.

Gap Period:

- Start = Visit end date of M24 Visit + 1
- End = Extension Study Baseline Visit start date

Year 3 Visit Period:

- Start = Visit end date of M24 Visit + 1
- End = Visit end date of M36 Visit

Year 4 Visit Period:

- Start = Visit end date of M36 Visit + 1
- End = Visit end date of M48 Visit

Year 3 Visit and Year 4 Visit Period (i.e., **Extension Study Period**):

- Start = Visit end date of M24 Visit + 1
- End = Visit end date of M48 Visit

After start of study medication until end of Year 3 Visit Period:

- Start = Start of study medication (see MAGNIFY MS IAP version 3.0 for definition)
- End = Visit end date of M36 Visit

After start of study medication until end of Year 4 Visit Period (i.e., **Parent and Extension Study Period**):

- Start = Start of study medication (see MAGNIFY MS IAP version 3.0 for definition)
- End = Visit end date of M48 Visit

In case of missing M48 Visit or early discontinuation before an End of Period defined above, the Visit end date of EW Visit will be used to replace the corresponding End date, or the study discontinuation date will be used if the EW visit was not performed.

In case of missing M36 Visit, the Visit end date of M36 Visit in the above definitions (including Start and End) will be replaced by MAGNIFY MS M24 Visit date + 480 days (which is obtained by 360 (12 months) + 90 (3 months delay allowed for FAS) + 30 (Visit window)), or the Visit end date of EW Visit if earlier, or date of discontinuation if earlier and the EW Visit was not performed.

Study Periods for MRI Assessments

The MRI scans in the parent study were reconciled during central MRI review process. Therefore, MRIs were considered as Baseline MRIs if assigned to the Baseline Visit by the central imaging review.

The following study periods for MRI assessments are defined as per MAGNIFY MS IAP version 3.0 with extension to Month 36 Visit and Month 48 Visit MRI scans:

Baseline Period (p₀): The Baseline Period is defined as the Period between the Screening and the Baseline MRI scan in MAGNIFY MS trial.

Post-Baseline Periods (ppost-Baseline):

Yearly Periods:

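### Primary NEDA-3 Kaplan-Meier estimate: the final scan is an event if active and a censoring if clean, on actual dates, so the 24-month proportion depends on when participants attended

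*SAP*

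**What the plan says.** SAP 14.1.1 takes the event date for MRI activity from the first scan showing a T1 Gd+ or active T2 lesion. A participant without any event is censored at the earliest of three dates: "the minimum of the scan date of the last available MRI, the assessment date of the last available EDSS", and the extension completion or discontinuation date. Time runs from the day after the M24 visit ends.

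The NEDA-3 proportion is "estimated as per the KM method and reported at 6-months intervals". Protocol 9.4.1 (Table 6) wants the KM estimate and 95% CI at the end of the two years. The SAP names no read-out day, but SAP 9.4 sets "1 month = 30.4375 days".

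SAP 9.5 schedules Visit 2 at "2 years (720 days) after M24 Visit", ± 30 days. Protocol 4.1 instead plans it at 24 months, as near the yearly date as possible. For late assessments SAP 9.5 says that "assessment data will be treated as though it occurred at the nominal time point specified", but adds: "The MRI assessment will be the only exception to this rule". SAP 9.8 keeps scans up to 185 days from the visit date. The substitute date for a missing M36 visit in SAP 9.6 includes "90 (3 months delay allowed for FAS", so some late attendance is expected.

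SAP 14.2.1 applies the same event and censoring rule to the Year 3, Year 4 and Day 1 NEDA-3 proportions.

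**The concern.** KM needs participants censored at a given time to have the same future risk as those still followed. Here that fails by construction. Among participants event-free up to Visit 2, a clean scan removes the person from the risk set and an active scan counts as a failure, on the scan date. Clean participants scanned early are gone when active participants scanned later are counted, so each later event is divided by a shrunken risk set. Active scans after the read-out day are not counted at all. The first effect lowers the estimate and the second raises it. Which one wins depends on how many final scans fall before day 730.5.

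This is not a missing-data problem: it occurs with full attendance, and the missing-at-random assumption in Protocol Table 6 does not cover it. Visit 1 causes no such difficulty in the primary analysis, because participants with a clean scan stay at risk.

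The study has one arm and no hypothesis test, so this proportion and its interval are the main result.

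**Working it through.** The visible text states no expected NEDA-3 proportion or precision, so there is no planned figure to reproduce.

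**Calendar (SAP 9.4, 9.5, 14.1.1)**
- Read-out: 24 × 30.4375 = day 730.5.
- Visit 2: 720 / 30.4375 = 23.66 months. The window of days 690–750 is 22.67–24.64 months, so the read-out lies inside it.

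**Assumptions (not in the documents)**
- N = 220 (upper end of the evaluable range in the protocol synopsis), everyone attends, no dropout.
- MRI activity 20% per visit; relapse rate 0.08 per year.
- Disability progression set to zero. A 6MCDP is dated at the earlier of two assessments at least 166 days apart, so it can hardly start at Visit 2 and is largely outside this mechanism.
- True NEDA-3 = 0.8 × 0.8 × exp(−0.08 × 720/365.25) = 0.64 × 0.854 = 54.7%.

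**Analytic check**

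Let F be the share of final scans done by day 730.5 and p the probability of an active final scan. Events accrue as p·dF on a risk set of about 1 − F, so the final-visit factor is about (1 − F)^p instead of 1 − p. The event-free share before Visit 2 is 0.8 × 0.854 = 0.683. With p = 0.20 and visit SD 10 days:

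| Centre | F | (1 − F)^0.2 | KM = 0.683 × factor |
|---|---|---|---|
| day 720 | 0.853 | 0.68 | about 47% |
| day 730 | 0.52 | 0.86 | about 59% |
| day 740 | 0.17 | 0.96 | about 66% |

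The correct factor is 0.80. It is matched only when 1 − F = 0.8^5 = 0.328, that is F = 0.672. Uniform attendance over days 690–750 gives F = 40.5/60 = 0.675, so its agreement with the truth is a cancellation.

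**Simulation of the SAP rule** (1,000 trials per pattern, log-log Greenwood CI, EDSS on the scan day, true 54.7%)

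| Attendance | Mean KM at day 730.5 | 95% CI coverage |
|---|---|---|
| Centre 720, SD 5 | 33.3% | 11% |
| Centre 720, SD 10 | 46.9% | 58% |
| Centre 720, SD 15 | 51.6% | 89% |
| Centre 720, SD 30 | 55.9% | 93% |
| Centre 720, uniform ± 30 | 54.5% | 96% |
| Centre 720, SD 15, 15% of visits 30–90 days late | 55.7% | 94% |
| Centre 730, all six spreads | 58.5–60.8% | 61–83% |
| Centre 740, all six spreads | 62.1–67.9% | 3–45% |

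Separate runs put the lowest figure at about 34%, hence the rounded range of 34–56% for centre 720.

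**Range over MRI activity** (SD 10, SD 15 and uniform ± 30; centres 720 / 730 / 740)
- 10% per visit, true 69.2%: 63.7–68.4 / 71.2–71.3 / 73.8–75.5%.
- 30% per visit, true 41.9%: 34.6–42.8 / 47.8–48.3 / 52.7–56.7%.

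**Year 3 and Year 4 proportions** (read at 12 × 30.4375 = day 365.25; true 0.8 × exp(−0.08 × 360/365.25) = 73.9%)
- Visits centred on 360/720: 63.8–78.0% (Year 3) and 68.6–78.7% (Year 4).
- Centred on 365/730: about 80% for both.
- Centred on 370/740: 82–89% and 82–87%.

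**EDSS dates (secondary).** Protocol 8.1 allows ± 5 days between assessments of one visit. An EDSS before the scan censors clean participants sooner. For centre 720, with EDSS on the same day versus 0–5 days before: 54.5 versus 27.1% if every scan is on day 720; 47.1 versus 43.8% at SD 10; 54.5 versus 53.7% for uniform ± 30.

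**The case against.** The mechanism is hard to dispute; its size is not. The lowest figures need very tight attendance: SD 5 puts about 95% of visits within ± 10 days, while the visit window, the delay allowance and the MRI tolerance all point to wider spread. With wide spread around day 720 the estimate is within about a point of the truth and coverage is 93–96%. This stands, and it is why the day-730 case, which matches calendar scheduling under Protocol 4.1, is the better guide. It does not remove the concern, because the agreement depends on F happening to be near 0.67.

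SAP 14.1.1 already plans numbers at risk and the proportions with an event and censored, and 14.1.2 adds crude percentages. With complete data the crude proportion is close to the right answer. That would show a reader the discrepancy, but the KM figure remains the primary estimate and nothing says which to believe. No hypothesis is tested and the interim analysis triggers no decision, so the harm is a misreported estimate, not a wrong decision rule.

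Three stronger readings are tempting:
- *The time-to-first-activity results in SAP 14.2.2 are equally affected.* They report percentiles and medians, not a proportion at a fixed day, so the read-out argument does not carry over.
- *The plan ignores informative censoring.* The SAP defines an abbreviation for censoring not at random and cites methods papers on it. Redacted text may use them, although 14.1.1 and 14.1.2 show none.
- *SAP 9.5 and 14.1.1 flatly contradict each other on EDSS dates.* The specific rule in 14.1.1 can be read as governing. A sentence on precedence is enough.

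**Conclusion.** The point holds. As written, the primary 24-month NEDA-3 proportion and its CI depend on attendance dates, and the bias can go either way. Mechanism and read-out day follow from the SAP text alone.

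The size rests on assumed activity rates and attendance. At 20% MRI activity it is about 4 to 6 points upward for visits centred on day 730, larger upward for day 740, and anything from about 21 points downward to 1 point upward for day 720. At 10% activity and centre 730 it is about 2 points. A reader might infer that the estimate must be badly wrong, or always too high; neither follows.

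The Year 3 and Year 4 proportions share the defect. The Day 1 proportions share the rule, but their bias was not quantified because the documents do not give parent-study visit timing.

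**What to change.** For the primary, Year 3 and Year 4 proportions:
- Date scheduled-visit MRI and EDSS events at the nominal day: 360 or 720 from M24, and 360 from M36 for Year 4.
- Censor event-free participants at the nominal day of the last visit with both a usable MRI and an EDSS. Attendance alone must not count: under the assumptions above, 10% missing final scans treated as clean would add 0.683 × 0.20 × 0.10 = 1.4 points.
- Count events before censorings at ties, and read the proportion at the nominal day.
- Place each relapse in the visit interval in which it occurred. One before the actual visit but after its nominal day takes the nominal day; one after the actual M36 visit is dated day 361 or later in the analyses from M24.
- Keep Early Withdrawal assessments at their actual dates here, as a stated exception to the SAP 9.5 rule that "The assessments of the EW visit will be mapped to the nearest planned post-baseline visit with a missing assessment".

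Alternatively, use an interval-censored (Turnbull) estimate with actual scan dates and a named read-out day. Use this for the Day 1 proportions, where days 360 and 720 do not apply. Keep the actual-date KM as a secondary plot. State whether the dating rule in 14.1.1 or the nominal-time rule in 9.5 takes precedence.

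With complete data, nominal dating gave 54.1–54.7% against 54.7% in 18 attendance patterns, with coverage 93.5–95.8%. Turnbull was within 1.6 points of the truth in six cases, on only 40 trials each.

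The cost is SAP wording and programming. Exact scan dates are not used. Early Withdrawal scans at actual dates leave a downward bias of about 0–1 point at 5–10% dropout and up to 2.4 points at 20%. Visits centred on day 740 lower the nominal estimate by about 0.9 points through extra exposure.

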5.1 Inclusion Criteria

Participants are eligible to be included in the study only if all the following criteria apply:

1. Participants of the MAGNIFY MS trial who received at least a single dose of cladribine tablets during the MAGNIFY MS trial and data on MRI is available/acquired from at least parent study Month 18 or Month 24 visit and EDSS and relapse from parent study Month 24 visit.

Informed Consent

2. Capable of giving signed informed consent, as indicated in Appendix 2, which includes compliance with the requirements and restrictions listed in the informed consent form (ICF) and this protocol.

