14.2 Secondary Endpoints

14.2.1 No Evidence of Disease Activity

As a secondary analysis, NEDA-3 during the following Periods (see definition in Section 9.6) will be analyzed similarly as in the primary analysis using the KM method:

Year 3 Visit Period

- Start date: end date of M24 Visit (see definition in Section 14.1.1) + 1
- Event date: same as in Section 14.1.1 accounting for events started during Year 3 Visit Period only
- Censoring date: the minimum of the scan date of the last available MRI during Year 3 Visit Period, the assessment date of the last available EDSS during Year 3 Visit Period, and the end date of Year 3 Visit Period (see definition in Section 9.6)

Year 4 Visit Period

- Start date: end date of M36 Visit + 1
- Event date: same as in Section 14.1.1 accounting for events started during Year 4 Visit Period only

• Censoring date: the minimum of the scan date of the last available MRI during Year 4 Visit Period, the assessment date of the last available EDSS during Year 4 Visit Period, and the Extension Study completion/discontinuation date

After start of study medication until end of Year 3 Visit Period

- Start date: date of Day 1 as defined in Section 9.5
- Event date: The event date will be defined as the minimum of
 - o the onset date of the first qualifying relapses during the Parent and Extension Study Period
 - o the start date of the first 6MCDP during the Parent and Extension Study Period
 - o the scan date of the first MRI during the Parent and Extension Study Period where at least one T1 Gd+ lesion or at least one active T2 lesion (see Section 9.8 for definition) is identified,

accounting for events started during "After start of study medication until end of Year 3 Visit Period" only.

• Censoring date: the minimum of the scan date of the last available MRI during "After start of study medication until end of Year 3 Visit Period", the assessment date of the last available EDSS during "After start of study medication until end of Year 3 Visit Period", and the end date of "After start of study medication until end of Year 3 Visit Period" (see definition in Section 9.6)

After start of study medication until end of Year 4 Visit Period (i.e. Parent and Extension Study Period)

- Start date: date of Day 1 as defined in Section 9.5
- Event date: same as for "After start of study medication until end of Year 3 Visit Period" accounting for events started during "After start of study medication until end of Year 4 Visit Period"

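### In the primary NEDA-3 analysis relapses count to the end of the period, but event-free participants are censored at their last scan; where scans are missing this censoring is informative, and no listed sensitivity analysis tests it

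*SAP*

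**What the plan says.** **Events.** SAP 14.1.1 takes the earliest of three dates. For relapse the date is "the onset date of the first qualifying relapses during the Extension Study Period". SAP 9.6 ends that period at the M48 Visit; if the visit is missing or the participant leaves early, "the Visit end date of EW Visit will be used to replace the corresponding End date, or the study discontinuation date will be used".

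**Censoring.** Without an event, the date is the earliest of completion/discontinuation and "the minimum of the scan date of the last available MRI, the assessment date of the last available EDSS". The summary table in 14.1.1 repeats the rule: "Participants experienced no event will be censored as defined above".

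**Time.** "The start date will be the end date of M24 Visit + 1", and time in months is "event date or censoring date as applicable – start date + 1]/30.4375".

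**Parallel rules.** SAP 14.2.1 restricts the scan for Year 3: "the scan date of the last available MRI during Year 3 Visit Period". SAP 14.2.2, which covers the same events, start date and period as the primary analysis, also restricts MRI and EDSS to the period. SAP 14.1.1 has no such restriction.

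**Sensitivity.** Protocol Table 6 (9.4.1) analyses NEDA-3 by Kaplan-Meier assuming missing at random and leaves methods for departures from that assumption to the SAP. SAP 14.1.2 lists a repeat on the Treatment Completer Set, a repeat by previous DMD treatment, and crude percentages with missing as a separate category.

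**The concern.** Kaplan-Meier needs a participant's time at risk not to depend on whether the event later happens. Take someone whose last scan is at M36 and who stays in the study to M48. A relapse at month 20 makes that person an event at month 20. With no relapse, the same person is censored at about month 12. Within this group, the only people at risk after month 12 are those who will relapse. SAP 14.1.1 chooses Kaplan-Meier in order to reduce the impact of missing information, and this is where the missing information enters.

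Missing scans with continued relapse reporting are foreseeable. Scans more than 185 days from the visit are dropped from all analyses (SAP 9.8). Scan timing after relapse treatment may be settled case by case (protocol 8.1.1.1). A withdrawal may be handled by telephone, without a scan (protocol 4.1).

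A second difficulty is what the censoring date is when an event-free participant has no extension scan at all. The result could be an invalid survival time in the primary analysis.

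**Working it through.** The documents show no NEDA-3 rate, missing-scan rate or precision figure (the sample-size section is redacted), so there is no stated figure to reproduce. All event and missingness rates below are assumptions.

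**1. The mechanism by hand.** Take 100 participants event-free at M36. Let a share m = 10% have no M48 scan, and let relapse risk in Year 4 be q = 8%.
- True relapse-free factor: 1 − 0.08 = 0.920.
- Plan: all 8 expected relapses count (7.2 with a scan, 0.8 without). The 9.2 non-relapsers without a scan leave at M36. The risk set is 90 + 0.8 = 90.8, and the factor is 1 − 8/90.8 = 0.912.
- Symmetric rule (events count only up to the last scan): 1 − 7.2/90 = 0.920.

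The ratio of plan to truth is 1/(1 + mq/(1 − m)) = 1/(1 + 0.008/0.9) = 0.991. For m = 20% and q = 12% it is 1/(1 + 0.024/0.8) = 0.971. It equals 1 when m = 0.

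**2. Over two years.** Simulation of 1,000,000 participants, scans at months 12 and 24, MRI activity 12% per year, missingness unrelated to relapse, disability progression not modelled. True NEDA-3 is exp(−2 × relapse rate) × 0.88²; for a rate of 0.10 this is 0.819 × 0.774 = 63.4%.

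| Relapse rate per year | M48 scan missing | No extension scan | True % | Plan % | Difference (points) |
|---|---|---|---|---|---|
| 0.10 | 0% | 0% | 63.4 | 63.4 | 0 |
| 0.05 | 5% | 0% | 70.1 | 69.9 | −0.2 |
| 0.10 | 10% | 3% | 63.4 | 62.4 | −1.0 |
| 0.20 | 15% | 7% | 52.0 | 48.9 | −3.1 |

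The symmetric rule shows no bias in these settings. A second grid (annual relapse risk 5 to 12%, MRI activity 10 to 20%, up to 20% without a Visit 2 scan and 10% with no extension scan) gives −0.4 to −3.0 points for the plan and within 0.1 for the symmetric rule. Censoring every event-free participant at study end is not a remedy: it overstates by 0.7 to 5.2 points over that grid.

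**3. Precision for comparison.** With N = 210 (the protocol synopsis plans 200 to 220 evaluable), 1.96 × √(p(1 − p)/N) is 6.2 points at 70.1%, 6.5 at 63.4% and 6.8 at 52.0%, before any loss from censoring.

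**4. No extension scan.** Protocol 5.1 admits a participant if "data on MRI is available/acquired from at least parent study Month 18 or Month 24 visit". Under the literal wording of 14.1.1 the last scan is then a parent-study scan. Time in days is scan date − (M24 end + 1) + 1 = scan date − M24 end:
- scan on the M24 end date: 0;
- scan 5 days earlier: −5;
- Month 18 scan only: about −180.

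Under the 14.2.2 wording the scan date does not exist. If the minimum is then taken over the remaining dates, the participant is censored near study end, and with 2 to 7% in this group the net bias runs from −0.6 to +1.0 points.

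**5. If relapse makes a missed scan 2 to 3 times likelier** (relapse rates 0.10 and 0.20):

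| Method | Rate 0.10 (%) | Rate 0.20 (%) |
|---|---|---|
| Truth | 63.3–63.4 | 51.9 |
| Plan | 62.0–62.1 | 49.9–50.0 |
| Symmetric rule | 64.3–65.5 | 53.4–55.1 |
| Missed scan status imputed | 63.3–63.4 | 51.9 |

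**The case against.** A reader might infer that NEDA-3 is biased downward by construction. The documents do not support that. The mechanism needs participants without a later scan who are still followed for relapse. Scans are scheduled at Visit 1 and at Visit 2/Early Withdrawal (protocol Table 2), normally within 5 days of the visit (protocol 8.1). Someone who misses M36 but has M48 is censored at M48 and loses no follow-up.

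Nor is the net direction fixed. Visit 2 falls on day 720 ± 30 (SAP 9.5), while 24 months is 24 × 30.4375 = 730.5 days. With visits spread evenly over that window, N = 210, 10% lacking the Visit 2 scan and 5% lacking any extension scan, the net bias is +1.4 to +2.3 points at day 720 and −1.7 to −1.9 at day 730.5. A progression first seen at Visit 2 cannot be confirmed within the period (SAP 14.1.1), which pushes NEDA-3 up.

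A reader might also take the zero or negative times as settled. They follow from one unqualified phrase, and 14.2.2 suggests that a restriction to the period was intended. What stands is an unresolved conflict whose effect on the estimate can take either sign.

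It is fair to add that the study is exploratory, single-arm and without a hypothesis test. The crude percentages and the counts of events and censorings will show part of the problem. None of these changes the censoring rule, so they mitigate the point without answering it.

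**Conclusion.** The point holds in a conditional form. The window for counting relapses and the censoring date do not match, so censoring is informative among participants who lack a later scan but remain under relapse follow-up. This mechanism alone lowers the NEDA-3 estimate by about 0.2 to 3 points under the assumed rates and by nothing when MRI is complete. The 3-point figure needs the extreme corner: relapse 0.20 per year with 15% and 7% missing. In every case the shift is smaller than the confidence-interval half-width, but it is systematic and would not show in the interval.

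The conflict between 14.1.1 and 14.2.2 is a separate defect and needs correcting whatever the size of the bias. The visible SAP contains no analysis for departures from missing at random, although its abbreviation list includes censoring at random and not at random and its references include two papers on sensitivity to censoring. Redacted sections may hold more. This is a change that should be made; it does not invalidate the study.

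**What to change.** 1. **Wording.** Align 14.1.1 with 14.2.2 by limiting the last available MRI and EDSS to the Extension Study Period. State that an event-free participant with no extension MRI or EDSS stays in the FAS count and is censored on the first day of that period (M24 Visit end + 1, not the parent-study Day 1 of SAP 9.5). This repairs invalid times; it does not remove the bias.
2. **Symmetric run in 14.1.2.** Count events of all three components only up to the participant's evaluable-to date (last MRI/EDSS in the period). Label it a bound, because it is biased upward if relapse makes a missed scan more likely (step 5).
3. **Imputation run in 14.1.2.** Follow relapse and EDSS to completion/discontinuation and multiply impute MRI activity (yes/no) for a missed M36 or M48 scan. State the imputation model and its covariates, and assign the nominal visit date to an imputed event. This supplies what protocol Table 6 promises. The near-exact recovery in step 5 reflects simple simulated data and should not be expected in full from real data.
4. **Report** how many participants lack the M48 scan only, and how many lack any extension scan.

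The cost is a change of SAP text and one or two extra runs on data already collected. A few observed relapses are left out of run 2.
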